3.1.4 Long-Term Follow-Up

The long-term follow-up period will start after the EOCT/end of additional cycles (EOAC)/early withdrawal (EW) Visit.

Tumour assessments will be performed every 3 months (± 2 weeks) until whichever occurs first: documented disease progression (radiological or clinical as per the investigator's judgment), 2 years after the EOCT/EOAC/EW Visit, withdrawal of consent, lost to follow-up or death.

Safety assessments, and the subject's status, will be performed every 3 months (± 2 weeks) until whichever occurs first: 2 years after the EOCT/EOAC/EW Visit, withdrawal of consent, lost to follow-up or death; please refer to Section 8.1.4.1.

After the long-term follow-up period is completed i.e. 2 years after the EOCT/EOAC/EW Visit, all subjects will be invited to participate in a safety surveillance study, as part of a separate study protocol. All subjects will be asked to sign a new informed consent form to enter this study. The purpose of the safety surveillance study is to monitor any long-term effects of ^{177}Lu -OPS201 up to 5 years from the first dose of ^{177}Lu -OPS201.

The schedule of assessments is provided in a flow chart (see Section 5.1) and is listed in Section 5.2. Unless otherwise specified, all assessments will be performed by the investigator or accredited study personnel.

Extra visits, examinations, tests and interventions can be performed at any time if clinically indicated, as judged by the investigator.

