3.1.6 Secondary Efficacy Endpoints

The efficacy endpoints are:

- (a) Objective tumour response based on RECIST v1.1 (CT/MRI scan)
- Best overall response (BOR)

The best overall response according to RECIST v1.1 is defined as the best response recorded from the initiation of treatment until the EOCT/ EOAC/EW Visit, prior to the assessment of PD. Confirmation of complete or partial response is not required.

The following table provides a summary of the overall response status calculation at each time point for subjects who have measurable disease at baseline:

Table 4 Time point response

Target Lesions	Non-Target Lesions	New Lesions[a]	Time Point Response (TPR)
CR	CR	No	CR
CR	NCRNPD	No	PR
CR	NE	No	PR[b]
CR	NA[c]	No	CR
PR	NE	No	PR[b]
PR	CR	No	PR
PR	NCRNPD	No	PR
PR	NA[c]	No	PR
SD	NE	No	SD
SD	CR	No	SD
SD	NCRNPD	No	SD
SD	NA[c]	No	SD
NE	Non-PD	No	NE
PD	ANY	Yes/No	PD
ANY	PD	Yes/No	PD
ANY	ANY	Yes	PD

CR: Complete Response, PR: Partial Response, SD: Stable Disease, PD: Progressive Disease, NE: Not Evaluable, NCRNPD: Non-CR/Non-PD, NA: Not Applicable.

- a Identification of new lesions at a post-Screening time point will result in a TPR of PD. If an identified new lesion subsequently becomes NE, the TPR will be recorded as PD unless the new lesion has proven to have resolved. Note: TPRs assessed after a progression event will not contribute to the determination of the Best Response.
- b If a non-target lesion is classified as NE, a designation of PR may be assigned based on information from the target lesions.
- c No non-target lesions identified at Screening.

When SD or Non CR/Non Progressive Disease is believed to be the best overall response, it needs to be assessed a minimum of 8 weeks [56 days] after start of treatment. Otherwise, the best overall response will be NE, unless any Progressive Disease was further documented, in which case BOR will be Progressive Disease.

- Overall Response Rate (ORR)

The Overall Response Rate (ORR) is defined as the proportion of participants who achieved a Complete Response (CR) or a Partial Response (PR) as best overall response according to RECIST v1.1 criteria in the ITT Set. Subjects with no tumour assessment after the start of study treatment will not be evaluated.

- Disease Control Rate (DCR)

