For investigator data, the DCR rate at selected timepoints (Month 12, 18, 24) will also be generated. For DCR at month 12 (resp. 18 and 24 month), the analysis will include all patients who are on study at month 12 (resp. 18 and 24 month) defined as 365 days – 28 days (resp. 545 - 28 and 730- 28) relative to the first dose or patients who had early PD or death prior to that time. The best overall response category of CR, PR or SD in patients who have not had an early PD or death up to the timepoint will represent the subjects with disease control

c) Sum of Diameters

Descriptive statistics and 95% CIs of the mean for percentage change from baseline will be calculated by study part, cohort (part B only) and overall at Follow-up Visit 2, EOCT, EOAC (if any) and Long-Term Follow-up visits on the ITT and PP sets. The length of the longest diameter will also be presented.

Percent change and best percent change in sum of diameters will be listed.

Percent change of sum of diameters according to RECIST ^{CCI} will also be plotted by study part and cohort (part B only) at Visit 2, EOCT Visit, EOAC Visit (if any) and Long-Term follow up visits 1 and 2 on the ITT set.

Waterfall plots presenting best overall response (RECIST ^{CCI}) versus best percent change from baseline of sum of target lesion diameters over the whole study will be performed on the ITT set.

d) Progression Free Survival (PFS) from independent central review and from investigator assessment

PFS, defined as the time from first study drug administration to progression or death which ever occur first, will be analysed.

Disease progression will be assessed by tumour response evaluation according to RECIST v1.1/ ^{CCI}, measured using the same imaging technique (ceCT scan or MRI) for each subject throughout the study.

Event dates are assigned to:

- The first time when progressive disease was noted, or
- Date of death.

In case of progressive disease followed by death, the first event will be considered in the analysis. The date of progression will be recorded as the date of the last radiographic evaluation included in the series for that assessment.

Censoring dates are defined in subjects with no progressive disease or death before end of study or withdrawal. In these subjects, the censoring date is defined as the last date on which overall

RECIST status was evaluable. This is taken to be the date of the last radiological assessment at which the target lesions were evaluated (see Table 7).

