Table 7 Censoring Rules for PFS

Reason for censoring	Rule
No screening evaluable[a] assessment	Date of first treatment administration
Two or more not evaluable (NE) consecutive assessments before progressive disease or death	Date of last evaluable disease assessment before the second NE assessment
No progressive disease	Date of last evaluable disease assessment
Treatment discontinuation for undocumented progression	Date of last evaluable disease assessment
Treatment discontinuation for toxicity or other reason	Date of last evaluable disease assessment
Initiation of medications or therapy not permitted during the study	Date of initiation of non-permitted medication or therapy

a An assessment is considered NE when no imaging/measurement is done at all at a particular time point, or only a subset of lesion measurements are made at the time point. The subject is considered NE at that time point.

For central reading assessments, patients will be censored at the timepoint of the last central assessment at or before EOCT/EOAC.

The PFS time will be calculated as the time from first administration of the study drug to either progressive disease or death as follows.

$$\text{PFS time (in months)} = [(\text{Date of event} - \text{date of first administration of study drug} + 1) / 30.4375]$$

Data will be analysed by study part, cohort (part B only) and overall part B on the ITT and PP sets. The distribution of PFS times will be estimated using the Kaplan Meier method for each study part, cohort (part B only) and overall Part B. The median PFS time will be presented with its associated 95% CI, together with the number and percentage of events, by study part, cohort (part B only) and overall. The results will also be presented graphically in Kaplan Meier plots.

Completely missing tumour data: when tumour assessment visits are completely missing, FDA Guidance “Clinical Trial Endpoints for the Approval of Cancer Drugs and Biologics” [4] states that "events occurring after two or more missed radiological assessments will be censored in the analysis at the last adequate assessment”.

This will be implemented as follows:

[figure not shown]

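### The PFS censoring table calls a partly measured scan not evaluable even where the response table scores it as progression, and the SAP does not say which rule prevails

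*SAP*

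**What the plan says.** **Response rule (SAP 3.1.6, Table 4).** Note a to the table states: "Identification of new lesions at a post-Screening time point will result in a TPR of PD". The row "ANY PD Yes/No PD" (target, non-target, new lesion, response) makes non-target progression decisive whatever the target lesions show. A time point is not evaluable (NE) overall in one row only: targets NE, non-targets not progressing, no new lesion.

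**Event rule (SAP 3.2.3(d)).** Progression is judged by RECIST v1.1. The event date is "The first time when progressive disease was noted, or" the date of death. Censoring dates are set for subjects with neither event. They fall on the last date when overall RECIST status could be evaluated, which the text equates with the last radiological assessment that evaluated the target lesions.

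**Censoring rule (SAP 3.2.3(d), Table 7).** Footnote a covers the case where "only a subset of lesion measurements are made at the time point. The subject is considered NE at that time point". Its marker sits on the row "No screening evaluable[a] assessment". Another row, "Two or more not evaluable (NE) consecutive assessments before progressive disease or death", censors at "Date of last evaluable disease assessment before the second NE assessment".

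**End of scanning (Protocol 3.1.4).** In long-term follow-up, tumour assessments stop at "documented disease progression (radiological or clinical as per the investigator's judgment", among other reasons.

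**The concern.** A subject may have one target lesion unmeasured and a new lesion on the same scan. Table 4 makes that time point progression; footnote a makes it NE. Nothing in the SAP ranks the two rules, so two programmers could produce different PFS data from the same scans.

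The combination is plausible. SAP 1.3.2.2 requires no measurement of non-target lesions, only a note of presence, absence or unequivocal progression, so their progression can be seen while a target measurement is missing.

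If the footnote is followed, a progression can drop out of PFS or move later. The same scan would still count as progression for best overall response (SAP 3.1.6), and it would end a response under SAP 3.2.3(g), which has no rule for NE scans. The endpoints would then disagree about one scan. PFS is also estimated by cohort, and most Part B cohorts plan three to five subjects (Protocol 3.1.2), so one reclassified event can visibly change a cohort's curve.

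**Working it through.** The documents state no figure for this point. The check sets the two rules side by side and then follows one subject through each.

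**1. Where the rules differ.** Take a time point at which the target lesions are incompletely measured, so that target status is NE. Cross this with five non-target states (CR, non-CR/non-PD, NE, not applicable, PD) and new lesion yes or no: 5 × 2 = 10 combinations. Table 4's non-PD entry is read here as covering the four non-target states other than PD.

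| Non-target state | New lesion | Table 4 | Footnote a |
|---|---|---|---|
| Any of the five | Yes | PD (5 combinations) | NE |
| PD | No | PD (1 combination) | NE |
| CR, non-CR/non-PD, NE, not applicable | No | NE (4 combinations) | NE |

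The rules conflict in 5 + 1 = 6 of the 10. This counts combinations; it says nothing about how often each occurs.

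**2. What happens to one subject.** Part A, nominal visits: Follow-up Visit 2 at week 12 (day difference 84), EOCT at week 24 (168), first long-term visit 12 weeks later at week 36 (252). Week 12 is evaluable without progression. At week 24 there is a new lesion and one target lesion is unmeasured. The SAP formula is PFS months = (event date − first administration date + 1)/30.4375, used here for censoring times as well.

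- Table 4 prevails: event at (168 + 1)/30.4375 = 5.55 months.
- Footnote prevails, with no later evaluable progression or death: week 24 is NE, and the row for subjects without progression censors at week 12, (84 + 1)/30.4375 = 2.79 months.
- Footnote prevails, and a complete scan at week 36 records progression: event at (252 + 1)/30.4375 = 8.31 months, so the event is delayed rather than lost.

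**3. When the event is lost.** One NE scan does not trigger the row for consecutive NE assessments. The event is lost in two situations. In the first, no later evaluable progression or death follows; this is possible in long-term follow-up because tumour scanning stops once the investigator documents progression. In the second, the scan forms part of a run of two NE assessments. That row is worded to censor even if progression or death comes afterwards.

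**4. Does other text settle it?** The event-date sentence and the restriction of censoring to subjects without progression point towards Table 4. The sentence that ties the censoring date to evaluation of the target lesions points towards the footnote. Table 8 and the paragraph introducing it deal with assessments that are completely missing, and none of the six scenarios has a partly measured scan. The question is left open.

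**The case against.** The strongest reply is that 3.2.3(d) decides events first. Progression is assessed by RECIST v1.1, which the SAP implements in Table 4; the event is the first progression noted; and Table 7 serves subjects who have none. On that reading a recorded progression is never overwritten by a footnote. Investigator assessment is primary under SAP 3.2.3, so if the investigator has documented radiological progression, it has been noted. This is the more natural intent, and it means that censoring is possible rather than certain. It does not remove the conflict, because the footnote assigns NE to the subject at the time point and the text never says that a partly measured scan can carry a progression.

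The footnote marker sits only on the screening row, so the note may have been meant for baseline. That is fair, but its wording speaks of any particular time point, and it is the only definition of NE in a table that has a further row depending on NE. It could also be taken to describe target status alone, leaving Table 4 to resolve the overall response; its last sentence, about the subject, goes further than that.

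A reader might infer that such progressions are always lost. The documents do not support this. The stop-at-progression rule belongs to long-term follow-up. In the core trial, Part B scans are scheduled at each cycle, with further scans at EOCT, EOAC or early withdrawal (Protocol 7.2.1). Follow-up of subject status continues after progression, so a later death can still supply an event.

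A reader might also put a percentage on the inflation of median PFS. That would need a rate of partly measured progression scans and a median PFS, and the documents give neither.

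**Conclusion.** Footnote a is wrong as written: it contradicts Table 4 for partly measured scans that show a new lesion or non-target progression, and no text ranks the two. The surrounding text leans towards counting the progression. If the footnote is applied literally, the progression can be censored at the earlier scan (no later evaluable progression or death, or a run of two NE assessments) or its event delayed. Either would tend to bias PFS upward.

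The size cannot be computed from the documents. The 5.55 and 2.79 month figures show how far apart the rules can put one subject. They assume nominal Part A visit timing and no later event, and they do not estimate the effect on the median. PFS is a secondary, descriptive endpoint with no formal testing (SAP 3.1.9), so this is a limited correction to a definition, worth making before the PFS data are derived.

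**What to change.** In SAP 3.2.3(d), state that Table 4 determines the time point response before Table 7 is applied. In footnote a, define NE as a Table 4 response of NE, or no imaging at that time point. Add that a new lesion or unequivocal non-target progression is a PFS event even when some target lesions are not measured. Adjust the sentence that ties the censoring date to evaluation of the target lesions so that it agrees.

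The cost is a few lines of SAP text and a check of the PFS derivation program. No new data, scans or reads are required, and the choice is removed from the point where outcomes are already visible.

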Visit 1: On Visit 1 Day 1, subjects will receive the first administration of ^{177}Lu -OPS201 followed by safety and extended dosimetry evaluations over 8 days, with additional laboratory safety tests repeated at Day 15 (± 2 days). At 4 weeks (± 5 days) after Visit 1 Day 1 (i.e. Follow-up Visit 1), the safety of the subjects will be assessed.

Visit 2: 8 weeks after Visit 1 Day 1 (+2 weeks or up to +4 weeks in case of AEs which have not adequately recovered) subjects will receive the second administration of ^{177}Lu -OPS201 followed by safety and dosimetry evaluations over 8 days, with additional laboratory safety tests repeated at Day 15 (± 2 days). At 4 weeks (± 5 days) after Visit 2 Day 1 (Follow-up Visit 2), the safety of the subjects will be assessed. Additionally, subjects will receive a CT/MRI scan to monitor the RECIST v1.1 status and tumour volume changes.

Visit 3: 8 weeks after Visit 2 Day 1 (+2 weeks or up to +4 weeks in case of AEs which have not adequately recovered), subjects will receive the third administration of ^{177}Lu -OPS201 followed by safety and dosimetry evaluations over 8 days, with additional laboratory safety tests repeated at Day 15 (± 2 days). At 4 weeks (± 5 days) after Visit 3 Day 1 (Follow-up Visit 3), the safety of the subjects will be monitored.

EOCT Visit: 8 weeks (± 5 days) after Visit 3 Day 1, the safety and efficacy of the treatment will be evaluated. Subjects enrolled in Part A after the protocol version (v6.0) comes into effect will receive a CT/MRI scan to monitor the RECIST v1.1 status and tumour volume.

Part B

[figure not shown]
Visit 1: On Visit 1 Day 1, subjects will receive the first administration of ^{177}Lu -OPS201 followed by safety and extended dosimetry evaluations over 8 days, with additional laboratory safety tests repeated at Day 15 (± 2 days). At Week 4 (Day 29 ± 5 days), Week 6 (Day 42 ± 5 days) (i.e. Follow-up Visit 1) and at intermediate timepoints, the safety of the subjects will be assessed.

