- h urine will be collected for the following time periods: Visit 1 only: 0 (start of the infusion) to 4 hours, 4 to 24 hours, and 24 to 48 hours postinfusion (only 0 (start of the infusion) to 4 hours for US and Canada sites).
- i blood sampling to determine TACs will be performed before the infusion (baseline), at the stop of infusion (0), 5, 30 minutes, 1, 4, 24, 48, 72 to 96 and 144 to 168 hours after the stop of infusion of ¹⁷⁷Lu-OPS201 (Visit 1). Blood sampling for Visits 2 and 3 will be performed before the infusion (baseline), at the stop of infusion (0), 1, 4, 24, 48, 72 to 96 hours and 144 to 168 hours postinfusion.
- j in selected sites only.
- CC1
- l blood samples for assessment of OPS201 plasma levels will be collected at Visit 1 (first infusion): before the infusion (baseline), at the end of the infusion (0), 5±1 minute, 30±3 minutes, 60±5 minutes and at 4 hours±10 minutes, 6 hours±30 minutes, 8 hours ±30 minutes, 24±1 hours and 48±1 hours after the administration of ¹⁷⁷Lu-OPS201.
- m Urine samples for assessment of OPS201 urine levels will be collected Visit 1 only at the following time periods: 0 (start of the infusion) to 4 hours, 4 to 24 hours, and 24 to 48 hours postinfusion (only 0 (start of the infusion) to 4 hours in US and Canada sites).
- CC1
- o at Follow-up Visit 2 only.
- p at baseline (before the infusion)
- CC1
- r ceCT/MRI not older than 1 month on Visit 1 Day 1. To be performed also at each cycle of therapy (+2 weeks or up to +4 weeks in case of AEs), at the EOCT/EOAC/EW visit (±5 days) and at each long-term follow-up visit (±2 weeks)

Screening Visit	Visit 1						FU Visit 1			Visits 2/3 + additional optional V4, V5[y]						FU Visits 2 + 3 + additional optional V4, V5[a]		EOCT/EW Visit during the Core Trial (±5 days) [b]	EOAC/EW Visit during additional cycles [b] [v]	LTFU Visits (up to 2 years)
	Week -4 to -1	Day 1	Day 2	Day 3	Day 4 to 5	Day 7 to 8	Day 15 (±2 days)	Day 29 (±5 days)	Day 42 (±5 days)	Day 1	Day 2	Day 3	Day 4 to 5	Day 7 to 8	Day 15 (±2 days)	Day 29 (±5 days)	Day 42 (±5 days)			

- s central read of ceCT/MRI is performed during Core Trial and additional optional cycles; local read is performed during the 2-year LTFU period. ⁶⁸Ga-PET scan may be performed during the treatment period (Core Trial and Additional Cycles) and the 2-year LTFU period, if deemed necessary by the investigator.

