Progressive Diseases (PDs) occurring after two or more missed radiological assessments will be censored in the analysis at the last adequate* assessment before the missing assessments: If a subject has one missed radiological assessment before a PD, the PD will be analysed as an event (i.e. a PD is analysed as an event if the previous radiological assessment was performed within approximately the last 6 months).

Table 8 Event status for various scenarios with missing data

Scan Time	FU Visit 2	EOCT/EOAC / EW Visit	Long-term Follow-up Visits n	Long-term Follow-up Visits n +1	Event status
Scenario 1	missing	PD			Event at EOCT/EOAC/EW visit
Scenario 2	missing	missing	PD		Censored at Baseline
Scenario 3	missing	SD	PD		Event at Long-term Follow-up Visit n
Scenario 4	missing	missing	SD	PD	Event at Long-term Follow-up Visit n+1
Scenario 5	SD	SD	missing	PD	Event at Long-term Follow-up Visit n+1
Scenario 6	SD	missing	missing	PD	Censored at FU Visit 2

e) Dosing and dosimetry in conjunction with tumour burden

A figure depicting the following relationship displaying the Pearson’s correlation coefficient (and the associated 95% confidence interval):

- CCI
 -
- 

f) Quality of life

- EORTC QLQ C30 v3.0

For QLQ C30 global health status score, functional scales scores and symptom scales scores, descriptive statistics and 95% CIs of the mean will be presented for the raw data and for the changes from baseline during treatment, by study part, cohort (part B only) and overall at each visit (Visit 1, 2, 3, optional visits (if any) and EOCT/EOAC Visits) on the ITT and PP sets.

For the evaluation of the QLQ C30 scores values at baseline the EORTC QLQ C30 Reference Values manual (Ref. 12) or a more up to date reference will be used.

- EORTC QLQ – GI.NET21 (2006)

For GI.NET21 endocrine symptoms scale score, G.I. symptoms scale score, treatment related symptom scale score, social function scale score, disease related worries scale score, muscle /bone pain symptom item, sexual function item, information/communication function item and body Image item, descriptive statistics and 95% CIs of the mean will be presented for the raw data and for the changes from baseline during treatment, by study part, cohort (part B only) and overall at each visit (Visit 1, 2, 3 and EOCT Visit) on the ITT and PP sets.

g) Duration of Response (DoR)

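### SAP Table 8 and the sum-of-diameters summary follow the Part A scan visits, and in the Part B treatment period the missed-scan count and the 6-month wording can classify the same progression differently

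*SAP*

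**What the plan says.** **Missed-scan rule (SAP 3.2.3(d)).** Progression "occurring after two or more missed radiological assessments will be censored in the analysis at the last adequate" assessment before the gap; after a single missed scan it stays an event. The same sentence then explains this in time: "a PD is analysed as an event if the previous radiological assessment was performed within approximately the last 6 months". Table 7 states the matching censoring reason by count alone: "Two or more not evaluable (NE) consecutive assessments before progressive disease or death".

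**Table 8.** Its columns are Follow-up Visit 2, one combined column for EOCT/EOAC/EW, and two successive long-term visits. Scenario 6, for example, is "Censored at FU Visit 2". There is no column for Visit 2, 3, 4 or 5.

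**Scan schedules.**
- Part A: the only on-treatment scan before EOCT is at Follow-up Visit 2 (SAP Table 2, footnote n). Protocol 3.1 limits the EOCT scan to "Subjects enrolled in Part A after the protocol version (v6.0) comes into effect".
- Part B: scans are done at Visits 2 and 3 before dosing (SAP 1.2.1). SAP Table 3, footnote r, adds "To be performed also at each cycle of therapy", at EOCT/EOAC/EW and at each long-term visit. The Table 3 CT/MRI row has no mark at the follow-up visits between cycles.

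**Diameter outputs (SAP 3.2.3(c)).** The summary is produced "at Follow-up Visit 2, EOCT, EOAC (if any) and Long-Term Follow-up visits". The plot in the same subsection names Visit 2 instead, and omits Visit 3.

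**The concern.** A missed-scan rule works only if it is counted against the scans that were due. Table 8 illustrates the rule on a visit at which Part B is not scanned, and the 6-month figure corresponds to one missed scan only when scans are about 12 weeks apart. On Part B's shorter treatment-period spacing, a programmer following the count and one following the time wording could classify the same subject differently.

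The treatment period matters most for the central read, because central-review PFS stops at EOCT/EOAC (SAP 3.1.6 and 3.2.3(d)). PFS is also reported by cohort, and every cohort except 3 and 6 enrols three to five subjects. One reclassified subject is therefore 1/5 to 1/3 (20% to 33%) of such a cohort.

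**Working it through.** **Inputs.**
- Cycle interval: 8 weeks, extendable by 2 or up to 4 weeks (SAP 1.2.1).
- Part A grid: baseline 0, Follow-up Visit 2 at Week 12, EOCT at Week 24 (SAP 3.2.14).
- Part B grid: baseline 0, Visit 2 at Week 8, Visit 3 at Week 16, EOCT at Week 24. With five cycles: EOCT combined with Visit 4 at Week 24, Visit 5 at Week 32, EOAC at Week 40.
- Long-term visits: from 12 weeks after EOCT/EOAC, then every 3 months (taken as 12 weeks).
- Baseline scan: up to 1 month old at Visit 1 Day 1; taken first as Week 0, then as 4 weeks earlier.
- Months = weeks × 7 / 30.4375, the divisor in the SAP's PFS formula.

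**Reproducing the 6-month figure.** On the Part A and long-term grid, one missed scan is 2 × 12 = 24 weeks = 168/30.4375 = 5.5 months (6 months at calendar 3-month spacing). Two missed scans are 3 × 12 = 36 weeks = 252/30.4375 = 8.3 months. A limit of about 6 months separates one from two, so the two forms of the rule agree there.

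**The same check on the Part B grid.**

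| Last scan | Missed | PD seen at | Gap | By count | By 6-month wording |
|---|---|---|---|---|---|
| Baseline | Visit 2 | Visit 3 | 16 wk = 3.7 mo | Event | Event |
| Visit 3 | EOCT | LTFU 1 | 20 wk = 4.6 mo | Event | Event |
| Baseline | Visits 2, 3 | EOCT | 24 wk = 5.5 mo | Censored | **Event** |
| Visit 2 (5 cycles) | Visit 3, EOCT/Visit 4 | Visit 5 | 24 wk = 5.5 mo | Censored | **Event** |
| Visit 3 (5 cycles) | EOCT/Visit 4, Visit 5 | EOAC | 24 wk = 5.5 mo | Censored | **Event** |
| Visit 2 (3 cycles) | Visit 3, EOCT | LTFU 1 | 28 wk = 6.4 mo | Censored | Borderline |
| Visit 3 (3 cycles) | EOCT, LTFU 1 | LTFU 2 | 32 wk = 7.4 mo | Censored | Censored |
| EOCT (3 cycles) | LTFU 1, 2 | LTFU 3 | 36 wk = 8.3 mo | Censored | Censored |

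**Sensitivity of the baseline-to-EOCT case.** The first figure takes the baseline scan at Week 0, the second takes it 4 weeks earlier.
- Cycles on time: 24 weeks (5.5 months), 28 weeks (6.4).
- Both cycles 2 weeks late: 28 weeks (6.4), 32 weeks (7.4).
- Both cycles 4 weeks late: 32 weeks (7.4), 36 weeks (8.3).

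The conflict is clear only at 24 weeks. It is borderline at 28, given that the limit is worded as approximate, and gone from 32.

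**Diameter summary.** A three-cycle Part B subject has 11 scheduled post-baseline scans (Visits 2 and 3, EOCT, eight long-term visits). The summary leaves out 2 of the 11, and these are both of the scans before EOCT.

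**The case against.** The best defence is that the count is evidently the operative rule. Table 7, the main sentence of 3.2.3(d) and all six Table 8 scenarios use it; the time wording is a parenthetical gloss marked as approximate. The conflict also needs an unusual history. Part B scans precede dosing, so in the baseline-to-EOCT case the subject would have been dosed at two consecutive cycles with neither scan done, and a subject who stops treatment still has an early-withdrawal scan 8 weeks after the last dose. All of this stands and limits the practical effect. It does not remove the defect: the SAP never says that the count overrides the gloss.

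A reader might infer more than the documents support:
- *That the Visit 2 and 3 scans go unused.* Overall response is tabulated at every visit, tumour volume at every scheduled visit, PFS events are dated at first progression, and the diameter plot names Visit 2.
- *That every Part B subject counts as missing at Follow-up Visit 2.* Table 8 gives illustrations, and nothing says that a scan never scheduled is a missed one.
- *That Part A progressions before v6.0 are wrongly censored.* This too requires reading an unscheduled EOCT scan as missed. SAP Table 2 marks CT/MRI at EOCT without distinction, and the number enrolled before v6.0 is not given. The point calls for clarification and is not a demonstrated error.

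One passage points the other way. The Part B biopsy footnote in Protocol Table 8 mentions a RECIST assessment at Follow-up Visit 2. The visit descriptions and the CT/MRI row do not support it, and it is probably leftover text.

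**Conclusion.** The point holds in a limited form. Table 8 and the diameter summary use a visit without a scheduled Part B scan and omit the Part B on-treatment scans. The two forms of the missed-scan rule give opposite results for near on-time 24-week gaps in the Part B treatment period, and they agree in long-term follow-up.

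The number of subjects affected cannot be derived. Part B's planned share, 40/55 = 73%, is the population in which the case could arise, not the number in which it will. PFS is secondary and descriptive, with no formal testing, so the effect is probably small overall, though it could be visible in a three-to-five-subject cohort. This rests on the scheduled weeks above. The list of tables and figures is redacted, so the visits in the output shells could not be checked.

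**What to change.** 1. In 3.2.3(d), state that the number of missed scheduled scans governs, and delete the 6-month wording or confine it to 12-week spacing.
2. Define a missed scan against each part's own schedule, and split Table 8 by part. Part B: Visits 2 and 3, EOCT, Visits 4 and 5 if given, EOAC, long-term visits. Part A: Follow-up Visit 2, EOCT, long-term visits, with EOCT not counted as missed for subjects who had no EOCT scan scheduled before v6.0.
3. In 3.2.3(c), use Visits 2 and 3 (and 4 and 5 if given) for Part B in the diameter summary, and set the plot's on-treatment visits by part: Follow-up Visit 2 for Part A, Visits 2 and 3 for Part B.

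A pure count has one consequence to accept knowingly. A Part A subject with no EOCT scan scheduled, last scanned at Week 12, missing LTFU 1 (Week 36) and progressing at LTFU 2 (Week 48), is an event after 36 weeks (8.3 months), while a Part B subject can be censored after 5.5 months.

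The cost is SAP wording, one table and the matching programming specification. No data collection changes.
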